10.2.3.2 Weaning (ICU)

After the stabilization period, VentaProst weaning procedures will be initiated when the clinical team determines the patient is hemodynamically stable enough to begin the weaning process. VentaProst weaning will occur from mechanical ventilation only. The table below shows the typical weaning steps for aerosolized Veletri from mechanical ventilation. If weaning from VentaProst occurs while on mechanical ventilation, doses will be decreased in 20% increments of the VentaProst equivalent dose. If the patient has been extubated and is on institution's standard of care delivery system for administering aerosolized Veletri, weaning will occur in accordance with each site's standard of care practice guidelines for weaning of aerosolized Veletri.

Weaning Guideline

Aerosolized Veletri (from Ventilator)	VentaProst (from Ventilator)
50 ng/kg/min	Dose Equivalence to aerosolized Veletri 50 ng/kg/min
40 ng/kg/min	80% of Dose Equivalence
30 ng/kg/min	60% of Dose Equivalence
20 ng/kg/min	40% of Dose Equivalence
10 ng/kg/min	20% of Dose Equivalence

Patients on mechanical ventilation will be weaned from VentaProst slowly due to concern that VentaProst is providing significant clinical benefit and to avoid a rebound effect. VentaProst weaning will be performed as per institutional guidelines for weaning of

inhaled Veletri, except that VentaProst doses will be decreased in increments of 20% of the VentaProst equivalent dose, with a minimum of 30 minutes between changes, down to 20% of the dose before discontinuation. The VentaProst weaning process should occur in isolation to other treatment changes (no changes in inotropes, pressors, or vasodilators).

Patients will be observed closely before, during and after dosing changes. In the event the patient demonstrates signs of hemodynamic instability (changes in combined hemodynamic parameters) or a decrease in oxygenation indicated by either arterial or central blood oxygenation saturation during downward titration, the VentaProst dose will be returned to its previous level. Once the patient has been stable for 15 minutes, repeat attempts at dose reduction may be undertaken. The process will continue until the patient is fully weaned from VentaProst. The patient will undergo the following study-related procedures and evaluations during VentaProst weaning:

- Stabilize the patient at each dose adjustment for at least 15 minutes
- Measure hemodynamic, oxygenation, and ventilator parameters before and at 15 to 30 minutes after each VentaProst dose adjustment and at 15 to 30 minutes after discontinuation of VentaProst
- Record all concomitant medications
- Record AEs

10.2.4 End of Study (ICU)

Once VentaProst dosing has been discontinued, the patient will undergo the following study-related procedures and evaluations within 24 hours of VentaProst discontinuation:

- Record all concomitant medications
- Record AEs
- Perform comprehensive physical examination
- Obtain vital signs and weight
- Perform 12-lead ECG
- Collect blood for clinical laboratory tests, including serum pregnancy test for women of childbearing potential

11. DATA QUALITY ASSURANCE

11.1 Data Collection

Investigator or designee will enter the information required by the protocol onto the eCRFs in accordance with the eCRF Completion Guidelines that are provided with the eCRFs. CRAs will visit each investigational site as frequently as documented in the monitoring plan to review the eCRFs for completeness and accuracy against the source documents. CRAs will highlight any discrepancies found in the documentation of study conduct and ensure that appropriate site personnel address the discrepancies.

11.2 Clinical Data Management

Data from eCRFs will be entered into a clinical database as specified in the data management plan. Quality control and data validation procedures will be applied to ensure the validity and accuracy of the clinical database.

11.3 Database Quality Assurance

All databases will be reviewed and checked for omissions, apparent errors, and values requiring further clarification using computerized and manual procedures. Data queries requiring clarification will be documented and returned to the investigational site for resolution. Only authorized personnel will make corrections to the clinical database, and all corrections will be documented in an audit trail.

12. STATISTICAL CONSIDERATIONS

12.1 Statistical Methods

A Statistical Analysis Plan will be developed that describes in detail the statistical methods to be used for analysis of this study and will be finalized prior to database lock.

12.2 Determination of Sample Size

The number of patients has been selected to enable an adequate clinical assessment of pharmacodynamics, safety, and tolerability parameters without presenting undue risk to a large number of patient's exposure to this investigational product.

12.3 Analyses Sets

All patients who are enrolled in the study and who receive at least one dose of VentaProst will be included in the intent-to-treat (ITT) analyses of pharmacodynamic and safety data. All available data will be used and missing data will not be estimated or carried forward in any statistical summary or analyses.

Descriptive summary statistics include the number of patients, mean, median, percent coefficient of variation (% CV) (if required), standard deviation, and minimum and maximum values (quantitative variables) or the number of patients and percentages by category (qualitative variables). Changes will be assessed as the difference between baseline measurements and the appropriate post-dose measurements unless otherwise specified. Individual patient listings of data will also be provided to allow for review of all pharmacodynamic, safety, and tolerability parameters.

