Criteria for Conversion to Conventional Therapy	
At any time during VentaProst administration, patients will be crossed over to standard therapy of aerosolized Veletri if they meet one or more of the following pre-defined criteria for a deterioration in their condition:
 
 • Severe postoperative mediastinal bleeding (> 500 mL/hr) • Hemoptysis • If a clinically inadequate response to VentaProst is observed, the patient may be converted back to aerosolized Veletri administered in accordance with each site's standard of care guidelines at the investigator's discretion 
Additionally, patients will be crossed over to standard of care therapy with aerosolized Veletri after extubation.

Statistical Methods	
All patients who are enrolled in the study and who receive at least one dose of VentaProst will be included in the intent-to-treat (ITT) analyses of pharmacodynamic and safety data. All available data will be used and missing data will not be estimated or carried forward in any statistical summary or analyses.
 
Descriptive summary statistics include the number of patients, mean, median, percent coefficient of variation (%CV) (if required), standard deviation, and minimum and maximum values (quantitative variables) or the number of patients and percentages by category (qualitative variables). Changes will be assessed as the difference between baseline measurements and the appropriate post-dose measurements unless otherwise specified. Individual patient listings of data will also be provided to allow for review of all

	
pharmacodynamic, safety, and tolerability parameters.
 
The number of patients has been selected to enable an adequate clinical assessment of pharmacodynamic, safety, and tolerability parameters without presenting undue risk to a large number of patient's exposure to this investigational product.
 
Further details will be included in the Statistical Analysis Plan.

Efficacy Analysis	Efficacy will be secondarily determined by summarizing success or failure to meet the pharmacodynamics goals of the study.
Safety Analyses	Safety data will be summarized using frequencies and incidence rates.

Table 1 – Schedule of Assessments and Procedures – Part I

Study Procedures	Screening	Intra-Operative	Aerosolized Veletri Treatment Period (OR/ICU)	VentaProst Treatment Period (ICU)	End of Study
Written Informed Consent	X				
Demographics	X				
Assign Patient ID	X				
Medical History	X				

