5.4.1 Criteria for Patient Conversion to Conventional Therapy

At any time during VentaProst administration, patients will be crossed-over to standard of care therapy with aerosolized Veletri if they meet one or more of the following pre-defined criteria for a deterioration in their condition:

- Severe postoperative mediastinal bleeding (> 500 mL/hr)

- Hemoptysis
- If a clinically inadequate response to VentaProst is observed, the patient may be converted back to aerosolized Veletri administered in accordance with each site's standard of care guidelines at the investigator's discretion

Additionally, patients will be crossed-over to standard of care therapy with aerosolized Veletri after extubation.

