10.1.4 VentaProst Treatment (ICU)

10.1.4.1 Dosing

Patients who demonstrate at least a 15% improvement in one or more hemodynamic parameters with aerosolized Veletri will be eligible to receive VentaProst. Patients will undergo the following study-related procedures and evaluations:

- Patients will be switched from aerosolized Veletri to receive a calculated equivalent starting dose of 17 ng/kg/min VentaProst while still on mechanical ventilation
- Patients will receive increases in the VentaProst dose in 20% increments (refer to VentaProst Pharmacy Manual) every 15 minutes until at least 90% of the hemodynamic effect observed with 50 ng/kg/min aerosolized Veletri is achieved. Once this has been achieved, the patient will remain on a stable dose of VentaProst for at least 15 minutes
- Measure hemodynamic, oxygenation, and ventilator parameters before and after each VentaProst dose
- Record all concomitant medications
- Record AEs

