12.5 Pharmacodynamic Analyses

12.5.1 Primary Endpoint

The primary efficacy endpoint of this study is to determine the equivalent dose of VentaProst necessary to achieve a hemodynamic parameter measurement that is not less than 90% of the effect observed with 50 ng/kg/min aerosolized Veletri.

Further details will be included in the Statistical Analysis Plan.

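### Part I has no rule for entering patients who leave VentaProst before the 90% match into the primary dose summary, so by default they contribute no value to it

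*Combined protocol and SAP*

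**What the plan says.** Section 12.5.1 gives the primary endpoint as "to determine the equivalent dose of VentaProst necessary to achieve a hemodynamic parameter measurement that is not less than 90% of the effect observed"; the reference is Veletri at 50 ng/kg/min, conventionally delivered. It then defers the method: "Further details will be included in the Statistical Analysis Plan".

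Part I dosing (section 10.1.4.1) starts at 17 ng/kg/min and rises in 20% increments every 15 minutes "until at least 90% of the hemodynamic effect observed with 50 ng/kg/min aerosolized Veletri is achieved". No other end to the titration is given there. Section 2.1 says the dose is not titrated down to match the Veletri response.

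Section 5.4.1 provides exits from VentaProst. Severe mediastinal bleeding and hemoptysis lead to cross-over. There is also a discretionary route: "If a clinically inadequate response to VentaProst is observed, the patient may be converted back to aerosolized Veletri". Finally: "Additionally, patients will be crossed-over to standard of care therapy with aerosolized Veletri after extubation".

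On analysis, section 12.3 says that enrolled patients "who receive at least one dose of VentaProst will be included in the intent-to-treat (ITT) analyses of pharmacodynamic and safety data". It continues: "All available data will be used and missing data will not be estimated or carried forward in any statistical summary or analyses". The planned statistics are n, mean, median, SD, %CV, minimum and maximum, with individual listings. The synopsis adds: "Efficacy will be secondarily determined by summarizing success or failure to meet the pharmacodynamics goals of the study".

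**The concern.** The endpoint is a dose that comes into being only when the match occurs. A patient who leaves before that has no equivalent dose, and section 12.3 rules out supplying one. Followed as written, the plan gives a mean or median over matched patients only, within an analysis set labelled ITT.

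The loss is unlikely to be random. An inadequate response at the doses tried is what a high dose requirement looks like. A higher requirement also takes more 15-minute steps, which leaves more time for extubation to intervene. Because conversion for inadequate response is discretionary and about three sites take part, a site that converts early would tend to yield a lower matched-only dose than one that keeps titrating, with the same drug effect.

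At stake is the study's one primary result: the VentaProst dose to be read as equivalent to Veletri 50 ng/kg/min.

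**Working it through.** The plan has no figure of its own to reproduce. Section 12.2 justifies about 10 patients per part on clinical grounds and gives no SD, dropout rate or non-match rate. Everything below that depends on such quantities is assumed.

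**Inputs from the protocol:** about 10 Part I patients (section 5); start at 17 ng/kg/min; 20% increments every 15 minutes; parameters measured 15 to 30 minutes after each dose (Table 1, note 10). I take a step as 20% of 17 = 3.4, giving 17, 20.4, 23.8, 27.2 and so on.

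**1. Chance of at least one unmatched patient among 10:** 1 − (1 − p)^10, for an assumed non-match rate p.
- p = 5%: 40%
- p = 10%: 65%
- p = 20%: 89%
- p = 30%: 97%

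**2. Example in which both summaries move (assumed data).** Four patients match at 17, two at 20.4, two at 23.8, and two are converted after being assessed as unmatched at 27.2.
- Matched only: mean (4×17 + 2×20.4 + 2×23.8)/8 = 156.4/8 = 19.55; median (17 + 20.4)/2 = 18.7.
- Two right-censored above 27.2: the proportion still unmatched is 6/10 after 17 and 4/10 after 20.4, so the median is 20.4. The mean is at least (156.4 + 2×27.2)/10 = 21.08.
- Ratios: 18.7/20.4 = 0.917; 19.55/21.08 = 0.927.

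**3. Example in which the median does not move (assumed data).** Required doses are 17 (three patients), 20.4 (three), 23.8 (two) and 27.2 (two). The mean is 214.2/10 = 21.42. Dropping the highest one, two or three patients gives 20.78, 19.98 or 19.43 (−3.0%, −6.7%, −9.3%). The median is 20.4 throughout.

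**4. Direction, by simulation** (400,000 patients per dose distribution). Assumptions: required dose lognormal with median 14 to 24 ng/kg/min and CV 30% or 50%; loss either by giving up above 23.8 or 27.2, or by a 10% or 20% chance of extubation per step. Selection is the matched-only mean minus the mean had everyone been titrated to a match. Net is the matched-only mean minus the true mean requirement.

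| Scenario | Unmatched | True mean | All titrated to match | Matched only | Selection | Net |
|---|---|---|---|---|---|---|
| Median 17, CV 30%, give up above 27.2 | 5.5% | 17.76 | 20.36 | 19.62 | −0.7 | +1.9 |
| Median 20, CV 30%, 20% extubated per step | 27.7% | 20.88 | 22.94 | 21.11 | −1.8 | +0.2 |
| Median 24, CV 50%, give up above 27.2 | 39.6% | 26.86 | 29.07 | 21.09 | −8.0 | −5.8 |

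Selection was negative in every scenario with losses (−0.16 to −9.4 ng/kg/min). Net ran from +3.6 to −7.2. With no losses at all, the floor at 17 and the upward-only steps alone added +1.8 to +4.4.

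**5. What an exit tells us.** If a patient leaves before the post-dose assessment at a given dose, non-match at that dose has not been shown. Take the eight matches of step 2, but let the two exits be bleeding before any assessment at 17. They carry no dose information, and the median stays at 18.7. Ranking them above all matches would give 20.4, which is 20.4/18.7 = 1.09, a 9% rise with no evidence behind it. Right-censoring and worst-rank are therefore different analyses.

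**The case against.** A reader might infer that the plan removes these patients. It does not say so: they remain in the ITT set, all available data are to be used, and section 12.5.1 defers the method to a SAP that is not in the text reviewed. A bound on the dose could even be argued to be available data. This stands as to wording. Omission is the default result of a sentence that covers any summary, not a written exclusion rule, and the point falls away if the SAP already handles these patients. Section 12.1, however, requires the SAP only before database lock, and in an open-label study a rule set after non-matches have been seen is less convincing.

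A reader might also infer that the reported dose is biased low. The documents do not support that. Only the selection component points down; the start at 17 without down-titration points up, and the balance depends on unknown quantities.

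It can also be said that failures will be visible through the reported n, the listings and the synopsis's success or failure summary. That is true, but these disclose the non-matches without correcting the dose.

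**Conclusion.** The gap is real, and closing it is a cheap improvement. By default the primary summary describes matched patients only, and the selection this causes is downward if exits for inadequate response, or during longer titration, go with higher dose requirements. The net direction for the reported dose is not established.

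The size cannot be derived from the documents. The shift of about 8% in the median and 7% in the mean comes from one assumed data set; in the other, the mean falls by 3% to 9% and the median is unchanged. Neither should be quoted as the expected effect. Nor should every exit be read as showing a requirement above the highest dose given: that holds only where a post-dose assessment showed less than 90% of the Veletri effect.

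**What to change.** In section 12.5.1 and the SAP, before data are reviewed:

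1. Report the number matched out of all Part I patients given VentaProst, with reasons for non-match.
2. For each unmatched patient, derive the highest VentaProst dose at which a post-dose assessment showed less than 90% of the Veletri effect, and enter the patient as right-censored above that dose. A patient who leaves before any assessment counts in the denominator of item 1 but gives no dose bound.
3. Treat patients who match at the first dose as at or below 17.
4. Make a censoring-aware median (interval-censored or Kaplan-Meier type) the primary summary. Give two sensitivity analyses: the matched-only summary, and a version ranking inadequate-response conversions above all matches. The second matters because a Kaplan-Meier type estimate assumes that converted patients resemble others still unmatched at the same dose, and they may need more.

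The cost is SAP wording and a derived variable. A CRF field for the reason for conversion may also be needed, since the discontinuation reasons in section 5.4 do not list extubation. The median may come out higher, or only as a bound. The dosing, titration and conversion rules are untouched.

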12.4 Demographic and Other Baseline Characteristics

Continuous demographic and other baseline characteristics (such as age, weight, and height) will be summarized using n, mean, SD, median, minimum, and maximum. Qualitative characteristics (such as gender and race) will be summarized by counts and percentages. Baseline hemodynamic parameters will be obtained prior to cardiac surgery with CPB.

12.5 Pharmacodynamic Analyses

12.5.1 Primary Endpoint

The primary efficacy endpoint of this study is to determine the equivalent dose of VentaProst necessary to achieve a hemodynamic parameter measurement that is not less than 90% of the effect observed with 50 ng/kg/min aerosolized Veletri.

Further details will be included in the Statistical Analysis Plan.

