Medication History	X				
Physical Examination	X				X
Vital Signs/Weight/Height	X				X ¹²
12-Lead ECG	X				X
Spirometry	X ¹¹				
Clinical Laboratory Sampling	X				X
Serum Pregnancy Test	X				X
Inclusion/Exclusion Criteria	X	X			
Cardiac Surgery with CPB		X			
Administer Aerosolized Veletri			X ⁶		
Administer VentaProst				X ⁹	
Hemodynamic Parameters ¹		X ⁵	X ^{7,8}	X ¹⁰	
Oxygenation Measurements ²			X ⁷	X ¹⁰	
Ventilator Parameters ³			X ⁷	X ¹⁰	
AE Monitoring ⁴		X			X
Concomitant Medications	X	X			X

¹ Hemodynamic parameters include, but not limited to, Cardiac Index (CI), Cardiac Output (CO), Central Venous Pressure (CVP), Diastolic Pulmonary Arterial Pressure (dPAP), Diastolic Systemic Arterial Pressure (dSAP), Heart Rate (HR), Mean Pulmonary Arterial Pressure (mPAP), Mean Systemic Arterial Pressure(mSAP), Pulmonary Capillary Wedge Pressure (PCWP), Pulmonary Vascular Resistance (PVR), Rhythm, Systolic Pulmonary Arterial Pressure (sPAP), and Systolic Systemic Arterial Pressure (sSAP)

² Oxygenation measurements include SaO₂ or SpO₂ and PaO₂

³ Ventilator parameters include Ventilator Type, Ventilator Mode, FiO₂, Inspiratory Time, Mean Airway Pressure, Peak Inspiratory Pressure, Positive End Expiratory Pressure, and Respiratory Rate

⁴ To include unanticipated medical events in the judgment of the investigator

⁵ Measure hemodynamic parameters prior to cardiac surgery with CPB and prior to dosing with aerosolized Veletri

⁶ Initiate aerosolized Veletri dose at 50 ng/kg/min in accordance with each site's standard of care guidelines and stabilize the patient on aerosolized Veletri for at least 15 minutes

⁷ Measure hemodynamic, oxygenation, and ventilator parameters after stabilization of aerosolized Veletri

⁸ Determination of hemodynamic response from baseline for study inclusion, study continuation, and transition to VentaProst

⁹ Initiate VentaProst dose at the calculated equivalent dose of 17 ng/kg/min; titrate up in 20% increments every 15 minutes (refer to VentaProst Pharmacy Manual); continue until dose is achieved that matches the hemodynamic measurements obtained with aerosolized Veletri dosing; stabilize patient on VentaProst for at least 15 minutes

¹⁰ Measure hemodynamic, oxygenation, and ventilator parameters before and at 15 to 30 minutes after each VentaProst dose (during dosing, stabilization, and weaning [if still intubated]) and at 15 to 30 minutes after discontinuation of VentaProst

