4. OVERALL STUDY DESIGN AND PLAN

4.1 Part I

The first part of this study will be conducted in approximately 10 consented post-operative cardiothoracic surgery patients on CPB who are receiving aerosolized Veletri (in accordance with each site's standard of care guidelines) and who demonstrate at least a 15% improvement in one or more hemodynamic parameters (as defined by the clinical team) when treated with aerosolized Veletri. This part of the study is designed to demonstrate the dose equivalence between aerosolized Veletri and VentaProst using a patient's hemodynamic parameters, with the goal to determine the VentaProst dose necessary to achieve a hemodynamic response that is not less than 90% of the effect observed with 50 ng/kg/min aerosolized Veletri. Arterial oxygen saturation (SaO₂) must be maintained at or above the level obtained with aerosolized epoprostenol administration.

Qualifying patients will:

- Receive aerosolized Veletri 50 ng/kg/min in the OR/ICU
- Have hemodynamic parameters measured before and after aerosolized Veletri administration to determine changes

- *IF AT LEAST A 15% IMPROVEMENT IN ONE OR MORE HEMODYNAMIC PARAMETERS (AS DEFINED BY THE CLINICAL TEAM) IS SEEN WITH AEROSOLIZED VELETRI AFTER STABILIZATION IN THE ICU:*
 - Be administered VentaProst as follows: Setup VentaProst inline to the ventilator circuit, start nebulization, then stop conventional Veletri pump flow and nebulizer while still inline. Do not remove Veletri administration system until VentaProst administration is confirmed
- *IF LESS THAN A 15% IMPROVEMENT IN ONE OR MORE HEMODYNAMIC PARAMETERS (AS DEFINED BY THE CLINICAL TEAM) IS SEEN WITH AEROSOLIZED VELETRI AFTER STABILIZATION IN THE ICU:*
 - Not be administered VentaProst
- Receive a calculated equivalent starting dose of 17 ng/kg/min of VentaProst while still on mechanical ventilation
- Receive increases in the VentaProst dose in 20% increments (refer to the VentaProst Pharmacy Manual) every 15 minutes until at least 90% of the hemodynamic effect observed with 50 ng/kg/min aerosolized Veletri is achieved

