10.1.2 Intra-Operative (OR)

The patient will undergo cardiac surgery with CPB in the OR and the following study-related procedures and evaluations:

- Measure hemodynamic parameters prior to cardiac surgery with CPB. These measurements will represent the baseline for hemodynamic parameters.
- Record all cardiovascular procedures and concomitant medications
- Investigator assessment of any unanticipated medical events

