10.1.3 Aerosolized Veletri Treatment (OR/ICU)

If there is a need for administration of aerosolized Veletri, the patient will begin dosing at 50 ng/kg/min (in accordance with each site's standard of care guidelines) and will undergo the following study-related procedures and evaluations:

- Measure hemodynamic, oxygenation, and ventilator parameters before aerosolized Veletri administration and after stabilization of aerosolized Veletri
- If at least a 15% improvement in one or more hemodynamic parameters (as defined by the clinical team) is seen with aerosolized Veletri after stabilization in the ICU, the VentaProst will be set-up inline to the ventilator circuit, VentaProst nebulization will be started, and then the Veletri pump flow will be stopped once VentaProst administration is confirmed. Do not remove Veletri administration system until VentaProst administration is confirmed
- If less than a 15% improvement is seen in one or more hemodynamic parameters (as defined by the clinical team) with aerosolized Veletri after stabilization in the ICU, the patient will not be administered VentaProst
- Record all concomitant medications
- Investigator assessment of any unanticipated medical events

If the patient does not require aerosolized Veletri, or if the patient fails to achieve at least a 15% improvement in one or more hemodynamic parameters with aerosolized Veletri, the patient will be withdrawn from the study as a screen failure.

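### Part I does not say whether the Veletri effect is measured from the pre-surgery or the pre-Veletri reading, or which parameter(s) decide the 90% match

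*Combined protocol and SAP*

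**What the plan says.** **Pre-surgery reference.** Section 10.1.2 schedules hemodynamic readings before surgery and adds: "These measurements will represent the baseline for hemodynamic parameters". Section 12.4 repeats it: "Baseline hemodynamic parameters will be obtained prior to cardiac surgery with CPB". Section 12.3 gives the general rule: "Changes will be assessed as the difference between baseline measurements and the appropriate post-dose measurements unless otherwise specified". Table 1 footnote 8 describes the Veletri-period reading as "Determination of hemodynamic response from baseline for study inclusion, study continuation, and transition to VentaProst".

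**Pre-Veletri reference.** Section 4.1 says patients will "Have hemodynamic parameters measured before and after aerosolized Veletri administration to determine changes". Section 10.1.3 says "Measure hemodynamic, oxygenation, and ventilator parameters before aerosolized Veletri administration and after stabilization of aerosolized Veletri", and its next bullet applies the 15% criterion. Table 1 footnote 5 collects both readings: "Measure hemodynamic parameters prior to cardiac surgery with CPB and prior to dosing with aerosolized Veletri".

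**Parameter.** Inclusion criterion 4c accepts a 15% improvement in any one or more parameters that the clinical team defines, and Table 1 footnote 1 gives an open list of candidates. Sections 7.1, 10.1.4.1 and 12.5.1 then set the target at 90% of the Veletri effect without naming a parameter; 12.5.1 words it as a "hemodynamic parameter measurement that is not less than 90% of the effect observed with 50 ng/kg/min aerosolized Veletri". Sections 6.2.1 and 6.3.3.1 speak in the plural of matching the PD measures achieved on Veletri. Section 4.1 also requires SaO2 to be held at the Veletri level, which limits the match but does not choose the parameter.

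**Timing.** Section 12.5.1 defers further detail to the SAP, which Section 12.1 has finalized before database lock.

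**The concern.** The Veletri effect is used at the bedside twice: to decide who crosses over to VentaProst, and to decide when open-label titration stops. Surgery and bypass come between the pre-surgery reading and the start of Veletri. A site that follows the protocol's named baseline would therefore attribute changes from surgery and bypass to Veletri. A site that follows 4.1 would not. Both could claim to be compliant and reach opposite decisions on the same patient.

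A later SAP cannot fully repair this. Under 10.1.3 a patient judged below 15% is withdrawn as a screen failure, and the analysis set in 12.3 holds only patients who received VentaProst, so no VentaProst data exist for that patient. A patient whose titration stops early never receives the higher dose. The recorded dose also sets the 20% weaning steps. Part I has about 10 patients and finding the equivalent dose is the sole primary objective, so a few patients scored on different definitions can move the summary.

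**Working it through.** The plan gives no calculated figure on this point, so there is nothing to reproduce first.

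**Inputs.** From the documents: 15% gate (inclusion 4c, 4.1, 10.1.3); 90% target (7.1, 10.1.4.1, 12.5.1); starting dose 17 ng/kg/min with 20% steps (4.1, 10.1.4.1). Not in the documents, so assumed: the shift between the two readings, and every patient value below.

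**Notation**, for a parameter where a fall is improvement: P is the pre-Veletri value, B = P(1 + s) the pre-surgery value, V = P(1 − e) the value on Veletri, and e the true Veletri fall.

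**1. The 15% gate.** Measured from B, a patient qualifies if V ≤ 0.85B, that is, if s ≥ (1 − e)/0.85 − 1.

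| True fall e | Smallest s that qualifies from pre-surgery |
|---|---|
| 0 | 1/0.85 − 1 = +17.6% |
| 15% | 0.85/0.85 − 1 = 0 |
| 20% | 0.80/0.85 − 1 = −5.9% |
| 30% | 0.70/0.85 − 1 = −17.6% |

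So a true 20% fall is rejected when the pre-surgery value is more than 5.9% below pre-Veletri, and a patient with no Veletri effect is accepted when it is at least 17.6% above.

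Invented patient: PVR 300 pre-surgery, 360 pre-Veletri, 290 on Veletri. From pre-surgery the fall is 10/300 = 3.3% (screen failure). From pre-Veletri it is 70/360 = 19.4% (qualifies).

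**2. The 90% stop.** With reference R, the stop value is V + 0.1(R − V). Changing R from P to B moves it by 0.1(B − P) = 0.1sP. Shifts of 10%, 20% and 30% therefore move the stop by 1%, 2% and 3% of the pre-Veletri value.

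Invented patient: PVR 360 pre-surgery, 300 pre-Veletri, 240 on Veletri. The stops are 240 + 0.1 × 120 = 252 and 240 + 0.1 × 60 = 246. If the pre-surgery value is no worse than the on-Veletri value, the effect from pre-surgery is zero or negative and the 90% target does not exist, but that patient also fails the gate on the same reference.

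**3. The parameter.** Invented patient, with PVR = 80 × (mPAP − PCWP)/CO and PCWP of 15, 14 and 15:

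| | Pre-Veletri | On Veletri | VentaProst 17 | Veletri effect | Share of effect at 17 |
|---|---|---|---|---|---|
| CO | 4.0 | 4.7 | 4.65 | 0.7/4.0 = 17.5% | 0.65/0.70 = 93% |
| PVR | 420 | 272.3 | 309.7 | 147.7/420 = 35% | 110.3/147.7 = 75% |
| mPAP | 36 | 30 | 33 | 6/36 = 17% | 3/6 = 50% |

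All three qualify. Judged on CO, titration stops at 17. Judged on PVR, on mPAP or on all three, it continues to at least 17 × 1.2 = 20.4 ng/kg/min.

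**4. Any versus all.** A simulation with 200,000 draws per setting assumed a true 20% Veletri effect, measurement error with SD 5% or 10% of the pre-Veletri value, correlation 0 or 0.5 between parameters, three candidate parameters, and a match judged on the qualifying ones only.

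| True effect of VentaProst 17, relative to Veletri | Match at 17 if any one suffices | Match at 17 if all must match |
|---|---|---|
| 70% | 37–47% | 5–16% |
| 100% | 64–82% | 24–37% |

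With a single fixed parameter the figures are 21–28% and 45–56%. Under these assumptions an any-one rule favours early stopping and an all-must-match rule favours further titration, so the choice needs to be stated.

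**The case against.** The best case for the plan is that its operative Part I rules already point to the pre-Veletri reading. Section 4.1 ties changes to before and after Veletri, 10.1.3 applies the gate directly after scheduling those readings, and 4c asks for a response to Veletri. Section 12.3 allows exceptions to its baseline rule, and 12.4 concerns baseline characteristics rather than bedside decisions. This is the sensible clinical reading, and nothing shows that sites would use the other. But footnote 8 governs this same decision and says baseline, 10.1.2 defines the hemodynamic baseline as pre-surgery, and no sentence settles which prevails.

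A reader might infer that the reference badly distorts the 90% match. In the 360/300/240 patient, 252 is 90% of the effect from pre-surgery but only 80% from pre-Veletri. That is correct arithmetic, but it describes a six-unit difference in the PVR stop, and no document supports any particular shift or direction.

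A reader might also infer that titration may stop on whichever single parameter looks best. The plural wording in 6.2.1 and 6.3.3.1 suggests instead that all qualifying measures must match, and under that reading the patient in step 3 would continue beyond 17. The objection stands to that extent; the wording only suggests the rule, and 7.1, 10.1.4.1 and 12.5.1 do not repeat it.

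Finally, part of the damage is recoverable. Readings are taken around every dose and individual data are listed, so over-titrated patients can be rescored at lower doses they received. Early stops and wrongly excluded patients cannot be recovered, and their frequency is unknown.

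**Conclusion.** The concern holds and should be fixed. The protocol names pre-surgery as the hemodynamic baseline while its design and procedure sections use pre-Veletri, and the conflict is not resolved. Its main consequence is at the 15% gate, where plausible-looking shifts in either direction reverse eligibility: below −5.9% for a true 20% fall, and at or above +17.6% for no effect. Its consequence for the 90% stop is small when both effects are positive. For the stop, the undefined parameter matters more, and it can change the recorded dose by at least one step.

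The thresholds are exact algebra. The shifts, patient values and simulation settings are assumptions, so none of this estimates how often a decision would change. The documents do not show that sites will use the wrong reading, or that one parameter such as PVR has to be imposed on every patient; that last is a design preference in a small, descriptive, open-label study.

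**What to change.** - In Table 1 footnote 8, inclusion 4c, 7.1, 12.5.1 and the bedside stop rule (4.1, 6.3.4.1, 10.1.4.1), define effect as the change, in the direction of improvement, from the last reading before Veletri.
- In 10.1.2 and 12.4, state that for Part I the pre-surgery value is descriptive only.
- Record the qualifying parameter(s) in the eCRF before VentaProst starts. Judge the 90% match on those same parameter(s), and state whether all must match.
- Report a match at the starting dose as 17 ng/kg/min or lower, because 2.1 rules out titrating down to find a smaller matching dose.

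The cost is a protocol amendment and one eCRF field. No new measurement is needed, since the pre-Veletri reading and the readings around each VentaProst dose are already scheduled.

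Two limits remain. Veletri may start in the OR while response is judged after stabilization in the ICU, so a pre-Veletri reference can still carry later intraoperative, transfer and recovery changes. And with patient-specific parameters, doses stay less comparable across patients than they would on one common parameter.
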